7 TRIAL PROCEDURES

7.1 Recruitment

7.1.1 Patient identification

Patients who may be eligible for the study will be identified by the Investigator from the site's records of patients with CHB. If a network of hospitals/clinics exists, other hospitals/clinics may identify suitable patients and refer them to the investigator's site.

7.2 Consent

Written informed consent will be obtained from all subjects at the screening visit, prior to entry into the study. The Investigator will explain to each subject orally and in writing the nature, significance, risks and implications of the trial before inclusion. In particular, the subjects will be informed about the following:

- the possibility of withdrawing from the clinical trial at any time by revoking the consent and without any resulting disadvantage.
- how personal and health-related data will be collected and used during the study.

All subjects will receive a copy of the subject information sheet and a copy of their signed and dated informed consent form (ICF).

7.2.1 Screening

The following screening assessments will be conducted between days -28 and -1:

- Sign informed consent
- Obtain medical history and demographic data
- Review of eligibility criteria
- Laboratory studies:
 - HBsAg monitoring
 - HBsAb monitoring
 - HBV DNA monitoring
- Vital signs
- Physical examination including measurement of weight and height
- Fibroscan
- Serum pregnancy test in women of childbearing potential
- Safety laboratory tests
- Urine dipstick test for drug abuse and alcohol screen
- Test for HIV, HDV and HCV
- Documentations of AEs
- Blood for cell-mediated immunity (CMI)
- 12-lead ECG

Patients who pass screening but are not dosed within 28 days may be re-screened once.

Subjects who have given their written informed consent will be allocated unique subject identification numbers in sequential order according to their admission to the study within each site by Interactive Response Technology (IRT). This number will be used for identification throughout the study and will not be used for any other participant.

7.3 The randomisation scheme

Subjects will be randomly assigned to 1 of 6 blinded treatment groups by the IRT into 3 cohorts as described in Table 2.

Following completion of the Screening activities, subjects who meet the all the inclusion and none of the exclusion criteria will be registered by the IRT.

The first subjects in each treatment arm of a cohort (i.e. active alone, active +IC31®, placebo and IC31® alone, as applicable) will form the sentinel group and, where possible, all sentinel subjects per treatment will be dosed at the same clinical site. Subsequently subjects in each cohort will be randomised to the applicable active or control treatment, to meet the required number of subjects to be dosed in each arm.

The randomisation list will be drawn up by an independent statistician.

7.3.1 Method of implementing the allocation sequence

After successfully completing the screening visit, subjects will be assigned a unique randomisation number in the order in which they are randomised. Randomisation numbers are provided in Table 3, these numbers are different to the subject identification numbers allocated at admission to the study.

Table 3 Randomisation Numbers

Cohort	Randomisation numbers	Sentinel randomisation numbers
1	1001–1018	1001–1002
2	2001–2036	2001–2004
3	3001–3018	3001–3002

7.4 Blinding

The Pharmacy staff will be unblinded for the purpose of final drug preparation. The pharmacist will consult the IRT for dose allocation and the Pharmacy staff will prepare each dose in compliance with the randomisation list.

Blinding of treatment assignment is critical to the integrity of this clinical study. Methods used to ensure blinding are described in the following paragraphs.

Due to the fact that formulations cannot be made to look identical, a double-observer technique will be used to maintain blind at the clinical site. Study staff either preparing the syringes and/or vaccinating the participants will be independent and will not take part in any other activity of the study (e.g. clinical assessments).

Injection materials and their labels should not be shown to subjects and subjects should be instructed to look away during the vaccination.

Knowledge of the randomisation list will be limited to the persons responsible for creation of the randomisation list, pharmacy staff who prepare the study treatments, and any unblinded study monitors or auditors, until all data has been entered in the electronic Case Report Form (eCRF), quality control and verification of the eCRF and assignment of subjects to the analysis populations has been completed, the database has been locked and the study formally unblinded.

Data provided to the SRC will be blinded.

7.5 Unblinding

If unblinding is required in the interest of the safety of a subject, an Investigator will discuss the matter with the Sponsor before using the IRT to unblind. In a medical emergency, the Investigator or delegate may unblind via the IRT for that subject without prior consultation with the Sponsor. In that event, the Investigator or delegate will notify the Sponsor as soon as possible that the randomisation code has been broken for the subject. If the blind is broken, the date, time, and reason must be recorded. For new patients, the method of unblinding for emergency purposes will be via the IRT.

7.6 Trial assessments

7.6.1 Safety assessments

7.6.1.1 Medical history

A complete medical history will be obtained at the screening visit and relevant medical history will be recorded in the eCRF. Enquiries will be made regarding all body systems including allergies/drug sensitivities, past surgeries, substance abuse and any other diseases or disorders.

7.6.1.2 Safety laboratory tests

Safety laboratory tests will be performed at the times indicated in the flow chart **Error! Reference source not found.** (see **Error! Reference source not found.** Table 1 Flow chart. At the screening visit the subjects will be screened for alcohol and drugs of abuse and infection with HIV, HDV and HCV. Further details are provided in Section 7.11.1.

The Investigator must review the laboratory report and document this review by signing the laboratory report form. Any clinically relevant values or changes in laboratory test values, as assessed against the normal reference ranges, must be recorded in the AE section of the subject's eCRF.

7.6.1.3 Vital signs

Vital signs will be measured at the times indicated in the flow chart (see Table 1 Flow chart). Vital signs include sitting blood pressure, pulse rate (after at least 5 min rest), and body temperature.

7.6.1.4 Electrocardiogram

A 12-lead ECG will be performed by the local site at the times indicated in the flow chart (see **Error! Reference source not found.**).

7.6.1.5 Physical examination

A physical examination will be performed by a physician at the times indicated in the flow chart (see **Error! Reference source not found.**). A full physical examination will be conducted at screening

including examination of weight and height, general appearance, eyes, ears, nose, throat, chest/respiratory system, heart/cardiovascular system, gastrointestinal system/liver, musculoskeletal system/extremities, dermatological system/skin, thyroid/neck, lymph nodes, and neurological system/psychiatric system.

A brief physical examination will be conducted at all other times including examination of general appearance, respiratory and cardiovascular systems and the abdomen, particularly the upper right quadrant. Any clinically relevant change in physical examination should be recorded as an AE.

7.6.1.6 Documentation of adverse events

See Section 9.

7.6.1.7 Documentation of local tolerability

Injection site tolerability will be assessed by the Investigator up to a minimum of 4 hours after the first injection and approximately 24 hours and 7 days after the first injection. For subsequent injections, injection site tolerability will be assessed by the Investigator up to 2 hours on the day of injection, 24 hours by means of a phone call and 7 days post injection.

Additionally, a diary card will be provided to the subjects to record injection site reactions from 4 hours (first injection) or 2 hours (subsequent injections) post injection to 7 days post injection. Data from the diary card will be transcribed into the appropriate eCRF.

The following solicited local injection site reactions will be assessed:

- Erythema/redness
- Swelling
- Induration/hardening
- Pain/tenderness (pain on pressure)
- Pain (spontaneous; pain without pressure)
- Pruritus/itching or burning sensation
- Wheal(s)

The symptoms will be graded as described in Table 4 Grading of solicited local injection site reactions.

Table 4 Grading of solicited local injection site reactions

	Grade 0	Grade 1	Grade 2	Grade 3	Grade 4
Erythema/redness	0-2.4 cm	2.5-5 cm	5.1-10 cm	>10 cm	Necrosis or exfoliative dermatitis
Swelling	0-2.4 cm	2.5-5 cm and does not interfere with activity	5.1-10 cm or interferes with activity	>10 cm or prevents daily activity	Necrosis
Induration/hardening	0-2.4 cm	2.5-5 cm and does not interfere with activity	5.1-10 cm or interferes with activity	>10 cm or prevents daily activity	Necrosis
Pain/tenderness (pain on pressure)	Absent	Mild discomfort to touch	Discomfort with movement	Significant discomfort at rest	Emergency room visit or hospitalisation
Pain (spontaneous; pain without pressure)	Absent	Does not interfere with activity	Repeated use of non-opioid pain reliever > 24 hours or interferes with activity	Any use of opioid pain reliever or prevents daily activity	Emergency room visit or hospitalisation
Pruritus/itching	Absent	Mild	Moderate	Severe	Not applicable
Wheal(s)	0-2.4 cm	2.5-5 cm	5.1-10 cm	>10 cm	Not applicable
Burning sensation	Absent	Mild	Moderate	Severe	Not applicable

Erythema, swelling, induration, tenderness, and pain are graded according to the FDA Guidance for Industry: Toxicity Grading Scale for Healthy Adult and Adolescent Volunteers Enrolled in Preventive Vaccine Clinical Trials (2007).

7.6.1.8 Additional safety examinations

If there are any unclear symptoms or observations the responsible physician in charge may perform further medical examinations, other than outlined in this protocol, including further clinical laboratory tests, in order to clarify the relevance or to diagnose symptoms.

7.6.2 Immunological and virological assessments

7.6.2.1 Determination of immunological parameters

Blood samples will be collected at the times indicated in the flow chart to evaluate CMI responses.

- IFN- γ ELISpot assay (ex vivo and cultured assay): to determine Vaccine FP-02.2-specific IFN- γ production from cryopreserved PBMC

- Other immunological assays may be performed such as T cell proliferation assays, intracellular cytokine assays, ELISA-based assays to measure Vaccine FP-02.2-specific antibodies, or other suitable assays to measure the immune response from PBMC or serum.
- The frequency of regulatory cells, expression of co-stimulatory and inhibitory markers may be measured by flow cytometry from cryopreserved PBMC.
- HLA genotyping will be performed on cryopreserved PBMC samples from consenting subjects to build an understanding of how the immune response to Vaccine FP-02.2 may or may not be independent of HLA genotype. Further genotyping may be performed from consenting subjects to assess the relationship between immune responses to the vaccine or HBV and associated gene profiles.

7.6.2.2 Determination of virological parameters

- Quantitative HBV DNA levels (PCR)
- Quantitative HBsAg levels (ELISA)
- Quantitative HBsAb levels (ELISA)

Immunological (IFNy ELISpot assay) and virological assessments will follow the OECD Principles of GLP.

7.6.3 **Assessment schedule**

Screening Visit

The screening assessment is described in Section 7.2.1.

Randomisation will be performed by IRT up to 3 days prior to first injection to allow data from screening to be available for confirmation of eligibility criteria and for the central pharmacy to supply medication to site.

Visit 1:

The following assessments and procedures will be performed on Day 1:

Pre-vaccination

- Review of eligibility criteria
- Urine pregnancy test in women of childbearing potential
- Blood for CMI
- HBsAg and HBsAb monitoring
- Vital signs
- Physical examination
- Documentation of concomitant medication
- Documentation of AEs
- Vaccination
- Contact IRT for drug supply
- Dispense diary card

Post-vaccination

- Injection site tolerability

- Documentation of concomitant medication
- Documentation of AEs

The subject will be asked to stay in the clinic for at least 4 hours following the first injection.

Visit 2

The following assessments and procedures will be performed on Day 2:

- Vital signs
- Physical examination
- Injection site tolerability
- Documentation of AEs and concomitant medications
- Review diary card for local tolerability

Visit 3

The following assessments will be performed on Day 8:

- Vital signs
- Physical examination
- Injection site tolerability
- Safety laboratory tests
- Documentation of concomitant medication
- Blood for CMI
- Documentation of AEs
- Review diary card for local tolerability
- Dispense new diary cards

Visits 4 and 6 (administration of booster vaccinations)

The following assessments will be performed on Days 29 and 57:

Pre-vaccination

- Urine pregnancy test in women of childbearing potential (pre-vaccination)
- Safety laboratory tests (pre-vaccination)
- Vaccination
- Vital signs
- HBsAg and HBsAb monitoring
- Physical examination
- Documentation of concomitant medication
- Documentation of AEs
- Blood for CMI

Post-vaccination

- Injection site tolerability (post-vaccination)
- Documentation of concomitant medication
- Documentation of AEs
- Dispense diary card

The subject will be asked to stay in the clinic for 2 hours after each booster vaccination.

Telephone Contact 24 hours after booster vaccinations

Telephone contact enquiring about AEs and injection site tolerability (assessed by subject) on days 30 and 58.

Visits 5 and 7

The following assessments will be performed on Days 36 and 64:

- Vital signs
- Physical examination
- Injection site tolerability
- Safety laboratory tests
- Documentation of concomitant medication
- Blood for CMI
- Documentation of AEs
- Review diary card for local tolerability

Visit 8:

The following assessments will be performed on Day 85:

- HBsAg and HBsAb monitoring
- Vital signs
- Physical examination
- Urine pregnancy test in women of childbearing potential
- Safety laboratory tests
- Documentation of concomitant medication
- Blood for CMI
- Documentation of AEs

7.7 Follow-up assessments

Subjects will be contacted (telephone call) by clinic staff at approximately 4-weekly intervals between Day 85 and Day 225 to check subject health.

Visit 9:

A follow-up visit will be performed at Day 225. The following assessments will be performed:

- HBsAg and HBsAb monitoring
- HBV DNA monitoring
- Vital signs
- Physical examination
- Safety laboratory tests
- Documentation of concomitant medication
- Blood for CMI
- 12-lead ECG
- Documentation of SAEs and AESIs (autoimmune disease and liver flares)

7.8 Qualitative assessments – Nested studies

Not applicable.

7.9 Allowed visit intervals

Allowed visit intervals are as follows:

- **screening and randomisation:** subjects must be screened 7 to 28 days (± 2 days) and can be randomised to treatment up to 3 days prior to the first injection.
- **first dose:** Visits 1 and 2 must be done on Days 1 and 2, respectively; Visit 3 may be done within ± 1 day of Day 8
- **second dose:** Visit 4 may be done within 28 days (± 7 days) of Visit 1; subjects must be phoned the day after Visit 4; Visit 5 should be done 7 (± 1 day) days after Visit 4
- **third dose:** Visit 6 may be done 28 days (± 7 days) after Visit 4; subjects must be phoned the day after Visit 6; Visits 7 and 8 should be done 7 (± 1 day) and 28 days (± 1 day) respectively after Visit 6
- **follow-up:** Visit 9 must be done 24 (± 4 weeks) weeks after the last dose (Visit 6)

The scheduled assessments may shift in instances where a visit window is used; subsequent visit dates should be recalculated from the date of the new visit. If a second dose visit is missed, the dose can be given 6 weeks after the first dose and noted as out of window. If the dose is later than 6 weeks, the second dose visit can be skipped and given at Visit 3 at 8 weeks as per schedule to avoid a delay in the schedule.

7.10 Withdrawal criteria

Participation in the study is strictly voluntary. A subject has the right to withdraw from the study at any time and for any reason. If he/she chooses to withdraw, the Investigator must be informed immediately. The Investigator has the right to terminate participation of any subject at any time if the Investigator deems it in the subject's best interest. The reason and circumstances for premature discontinuation will be documented in the subject's eCRF.

In general, all subjects should be encouraged to continue follow up until the end of the study even if they are withdrawn from continued study treatment, to allow collection of late safety data as well as immunogenicity and virology data.

7.10.1 Possible reasons for discontinuing subjects from continued study treatment

Examples of possible reasons for premature withdrawal of subjects:

- Major protocol violations;
- Pregnancy;
- Serious intercurrent illness;
- AEs which, in the judgement of the PI or Co-Investigator and subject to discussion with the Sponsor's medical advisor, justifies discontinuation;
- Non-compliance with study requirements;
- Withdrawal of consent by the subject;
- Subjects experiencing clinically significant injection site reactions or clinically significant changes in haematology and serum biochemistry results, considered possibly related to administration of the IMP, after a dose may not receive the subsequent dose of medication, at the discretion of the PI, in discussion with the Chief Investigator (CI) or the Sponsor's medical advisor. However, safety, virology and immunogenicity data will continue to be collected until the end of the study unless the subject withdraws his/her consent.

If a subject is withdrawn from study treatment, relevant study procedures e.g. physical examination, clinical laboratory analyses for safety and immunogenicity will be performed wherever possible. The reason(s) for discontinuation will be recorded in the appropriate section of the eCRF. Any subject who prematurely terminates participation and who has received at least one injection of the study treatment will undergo relevant post-study procedures for reasons of medical prudence, including a final examination and safety laboratory studies, unless the subject has withdrawn his/her consent and refuses to be examined and/or have blood drawn.

If a subject terminates participation due to an AE possibly related to the study medication or study procedures, the subject should be followed up by additional examinations according to the medical judgment of the Investigator until the abnormal condition is resolved or the Investigator deems further observations or examinations to be no longer medically indicated. If the subject refuses to be followed up the Investigator should explain the importance of the follow-up and encourage the subject to allow follow up. Subjects who elect to discontinue dosing should be encouraged to continue with other study procedures until the end of study if they are willing.

Study stopping rules

Individual subjects

An individual subject will have treatment discontinued if he/she experiences any one or more of the following events:

- ALT \geq 10 times the ULN
- INR $>$ 1.3
- Total bilirubin >3 times the ULN

Study as a whole

Dosing will be stopped for all subjects and enrolment discontinued if 20% or more of subjects experience one or more of the following events

- ALT \geq 10 times the ULN
- INR $>$ 1.3
- Total bilirubin >3 times the ULN
- Serious adverse events considered related to investigational products

- Severe systemic reactions.

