11 AUG 2016

Name (please print):

Position:

Signature of the Site Principal Investigator:

I agree to the terms of this Protocol and all amendments. I will conduct the study according to the procedures specified herein, and according to the principles of Good Clinical Practice (GCP) and local regulations.

Site No.:

Signature:

Date:

...../...../.....

Name, Title (please print):

Address:

Telephone number

KEY TRIAL CONTACTS

Chief Investigator	[name], MB BS MD FRCP Department of Hepatology Imperial College London St Mary's Campus [name]. [contact] E-mail: [contact]
Sponsor	Altimmune London Bioscience Innovation Centre [name]
Sponsor contacts	[name]; [name] PhD Altimmune UK Ltd. [contact] [contact] E-mail: [contact]; [contact] [name]. Altimmune, Inc. [name] [contact] ext 33 (office) [contact] (mobile) E-mail: [contact]
Sponsor Medical Advisor	[name], BMedSci, BMBS ProPharma Partners Limited [name] [contact] (out of hours) [contact] (working hours) Mob: [name] E-mail: [contact]
Pharmacovigilance (serious adverse event reporting)	PRA Health Sciences Safety and Risk Management [contact] [contact] (EAPA) E-mail: [contact]
Funder(s)	Altimmune UK Ltd./ Altimmune Inc
Sponsor contact for IMP	[name] PhD [contact] [contact] E-mail: [contact]

TRIAL SUMMARY

Trial Title	A phase I, randomised, double-blind, placebo-controlled, multi-centre, ascending-dose trial to evaluate the safety, tolerability and immunogenicity of Vaccine FP-02.2 in HBeAg-negative hepatitis B patients as an add-on treatment to entecavir or tenofovir.	
Internal ref. no.	FP-02.2_CS_01	
Clinical Phase	Phase I	
Trial Design	Randomised, double-blind, placebo-controlled, multi-centre, ascending-dose	
Trial Participants	Hepatitis B-infected, HBeAg-negative patients, aged 18-65 years, receiving on-going treatment with entecavir or tenofovir for at least 2 years	
Planned Sample Size	Approximately 60 subjects equally randomised between 6 treatment arms with 10 subjects per arm.	
Treatment duration	Subjects will receive 2 months active treatment (3 injections administered 28 days apart, i.e. over a period of 56 days). Subjects will be followed up 6 months after the last injection.	
	Objectives	Outcome Measures

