- Bloods for assessing liver function will be taken at 7 days after each injection and prior to the subsequent injection. These results will be reviewed by the Principal Investigator (PI) for each site. Any subject experiencing an increase in alanine aminotransferase (ALT) to 10 times the upper limit of normal (ULN), a prothrombin time, reported as the international normalised ratio (INR) of more than 1.3 or a total bilirubin greater than 3 times the ULN, will be called back to study site for assessment and will not receive any more doses of Vaccine FP-02.2. Subjects with an ALT above 5 times the ULN will be closely monitored and dosed at the discretion of the Investigator.
- Any subject experiencing a flare with decreased liver function will be managed by the PI for the site, as per local clinical protocols.
- A safety review committee (SRC) (defined as the country CIs, if applicable, and the study medical monitors) will review and assess all safety data for Cohorts 1 and 2 after at least 15 or 30 subjects, respectively, have completed Day 36 assessments.

Communication between the sites to discuss subject safety is of critical importance and, in addition to the SRC. Sites are encouraged to contact the Sponsor's medical monitor or regional CIs for any questions or concerns about the study, especially if related to patient safety.

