2.1.6 Dose escalation

For reasons of participants' safety, the clinical trial design will be performed in a stepwise fashion introducing each component based on the determined risk attributed to that cohort's treatment. Table 2 outlines the dosing regimen.

Table 2 Dosing regimen.

Cohort	Treatment arm	Approximate number of subjects
1	Placebo	5
	FP-02.2 Low-dose	10
2	Placebo	5
	IC31® adjuvant only	5
	FP-02.2 Low-dose + IC31® adjuvant	10
	FP-02.2 High-dose	10
3	IC31® adjuvant only	5
	FP-02.2 High-dose + IC31® adjuvant	10

For each cohort, the first subject from each treatment arm will form a sentinel group, e.g. for Cohort 1, the sentinel group will consist of 1 subject receiving placebo and 1 subject receiving Low-dose Vaccine FP-02.2. The CI and any PI(s) involved in dosing sentinel subjects will review safety data collected up to and including Day 8 visit as detailed in Section 4 before recommending whether or not the remaining subjects of a cohort should be dosed.

In order to escalate between doses, the SRC will review safety and tolerability data up to and including the Day 36 visit from subjects in Cohort 1 and verify no safety concerns have been detected before enrolling subjects into Cohort 2. Similarly, subjects may be enrolled into Cohort 3 after review of safety and tolerability data up to and including Day 36 from subjects from Cohort 2. If safety and tolerability data are not acceptable the SRC may recommend lowering the dose of FP-02.2 or omitting the use of IC31®.

All data used to support dose escalation will be quality checked. Dose decisions between cohorts will be documented.

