The first cohort starts with a low dose of Vaccine FP-02.2, 150µg/peptide (1350µg total peptide or placebo). The next cohort receives a higher dose of Vaccine FP-02.2, 500µg/peptide (4500µg total peptide) or a low dose of Vaccine FP-02.2, 150µg/peptide, in conjunction with 500nmol/20nmol KLK/ODN1a IC31® or placebo or 500nmol/20nmol KLK/ODN1a IC31® alone. The final cohort will test the high dose of Vaccine FP-02.2, in conjunction with 500 nmol/20 nmol KLK/ODN1a IC31® or 500nmol/20nmol KLK/ODN1a IC31® alone. See Table 2.

For each cohort, dosing will start with a sentinel group consisting of one subject from each treatment arm, receiving active or control (FP-02.2 (IC31®), IC31® or placebo), e.g. for Cohort 1, the sentinel group will consist of 1 subject receiving placebo and 1 subject receiving Low-dose Vaccine FP-02.2. After the assessments on Day 8, the SRC will meet and review the safety data from the sentinel group and recommend whether or not the remaining subjects of a cohort should be dosed. Any PI with patients in the sentinel group will provide input to the SRC meeting.

In order to progress to the next cohort, the SRC with input from the Investigators contributing patients will meet to review safety data up to Day 36 from Cohort 1. Following this review subjects may be dosed in Cohort 2 assuming the SRC has identified no safety concerns. Similarly, subjects may be dosed in Cohort 3 after review of safety data up to and including Day 36 from subjects in Cohort 2.

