7.10.3 Study termination

The Sponsor reserves the right to modify or terminate the study at any time. All subjects recruited to the study prior to termination, including those who have been withdrawn, will be followed until 225 days after their last injection.

Possible reasons for termination are:

- Safety reasons –the incidence of AEs in this or any other study using the same IMP indicates a potential health risk for the subjects.
- New scientific knowledge becomes known that makes the objectives of the study no longer feasible/valid
- Unsatisfactory enrolment of patients

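### The 20% study-wide halt has no denominator: counted over the whole study it is nearly inert for events confined to High-dose + IC31, and counted over subjects dosed to date it can stop the trial on one early event

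*Protocol*

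**What the plan says.** Protocol 7.10.1, under the Study as a whole subheading, reads: "Dosing will be stopped for all subjects and enrolment discontinued if 20% or more of subjects experience one or more of the following events". The listed events are ALT at least 10 times the upper limit of normal (ULN), INR above 1.3, total bilirubin above 3 times ULN, related serious adverse events, and severe systemic reactions. No denominator is given there or anywhere else in the Protocol or SAP.

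The Trial Summary plans "Approximately 60 subjects equally randomised between 6 treatment arms with 10 subjects per arm". Table 2 of Protocol 2.1.6 divides these into cohorts of 15, 30 and 15. High-dose + IC31 is 10 of the 15 in Cohort 3, which is dosed last, because "the clinical trial design will be performed in a stepwise fashion introducing each component".

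The other safety provisions are these:
- Individual stopping on the three liver criteria (7.10.1): "An individual subject will have treatment discontinued if he/she experiences any one or more of the following events".
- Liver tests 7 days after each injection and before the next (2.1.4).
- Sentinel review after Day 8 (section 4): "For each cohort, dosing will start with a sentinel group consisting of one subject from each treatment arm". The dose may be reduced afterwards (8.7).
- A Day 36 review in which the SRC will "review and assess all safety data for Cohorts 1 and 2 after at least 15 or 30 subjects, respectively, have completed Day 36 assessments" (2.1.4).
- Chief investigator oversight of risk and benefit (9.4) and urgent safety measures (9.8).
- Sponsor termination (7.10.3), for example if "the incidence of AEs in this or any other study using the same IMP indicates a potential health risk for the subjects".

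On what the SRC sees, section 7.4 says: "Data provided to the SRC will be blinded". SAP 10.1.2 has it work from listings and sets no count.

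**The concern.** This is a first-in-man study, and Protocol 2.1.2 and 2.1.4 name hepatic flare as the theoretical hazard. The 20% rule is the only numeric halt at trial level. The last escalation step joins the higher vaccine dose to the adjuvant, and that arm is one sixth of the planned total. A 20% threshold taken over everyone is larger than the arm itself.

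The missing denominator also cuts the other way. If subjects dosed to date are counted, the first few subjects carry so much weight that a single event meets the threshold. Two teams applying 7.10.1 in good faith could reach opposite decisions on the same data.

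**Working it through.** **Inputs.** Threshold 20% (Protocol 7.10.1). Arm and cohort sizes from Table 2 of Protocol 2.1.6, with allocation ratios in SAP 6.2. Replacement of subjects withdrawn before dose 2 (Protocol 7.10.4). The documents give no background rate for the listed events, so 0% to 10% is assumed below.

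**The plan's own total.** (5+10) + (5+5+10+10) + (5+10) = 60, as stated. The smallest count that meets 20% is 0.20 × 60 = 12.

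**Events confined to High-dose + IC31, all 10 affected, no replacements.**
- Planned total: 10/60 = 16.7%.
- Dosed to date, no Cohort 3 control yet dosed: 10/(45+10) = 10/55 = 18.2%, the maximum. With the control sentinel counted: 10/56 = 17.9%.
- Protocol section 1 gives 72 subjects instead, or 12 per arm if equal: 12/72 = 16.7%, against a trigger count of 15 (0.20 × 72 = 14.4).

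**With replacements counted.** Twelve affected reach 20% with up to three Cohort 3 controls dosed (12/60 = 20.0%) but not with five (12/62 = 19.4%). Thirteen affected with five controls give 13/63 = 20.6%. That would use all 18 Cohort 3 randomisation numbers in Protocol Table 3. If those 18 follow the 2:1 ratio, there are 12 active and 6 control, and 12/63 = 19.0%.

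**Narrower denominators, which the text does not state.** Vaccine recipients 10/40 = 25%; Cohorts 2 and 3 10/45 = 22.2%; Cohort 3 alone needs 3 of 15; the arm alone needs 2 of 10. All of these can fire.

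**Events in other arms.** With background rate b in the other 50 subjects and rate p in the arm, the halt probability is P(Bin(50,b) + Bin(10,p) ≥ 12):

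| Arm rate p | b = 0 | b = 2% | b = 5% |
|---|---|---|---|
| 100% | 0 | 0.26 | 0.72 |
| 80% | 0 | 0.06 | 0.30 |
| 50% | 0 | 0.002 | 0.04 |

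**Early in the trial, dosed to date.** One event among the two Cohort 1 sentinels is 1/2 = 50%. One among the first five subjects is 1/5 = 20%. Either meets the threshold.

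**A cohort trigger at 20% of planned size.** The ranges are for b from 0 to 5%, and events are counted over the whole cohort.

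| Cohort and trigger | p = 20% | p = 30% | p = 50% |
|---|---|---|---|
| Cohort 3: P(Bin(5,b) + Bin(10,p) ≥ 3) | 0.32-0.40 | 0.62-0.67 | 0.95-0.96 |
| Cohort 2, one 10-subject arm affected: P(Bin(20,b) + Bin(10,p) ≥ 6) | not computed | 0.05-0.19 | 0.38-0.60 |

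**False triggers when every arm has only the background rate.** The chance for any cohort is 1 − [1 − P(Bin(15,b) ≥ 3)]² × [1 − P(Bin(30,b) ≥ 6)].

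| b | 3 of 15 | 6 of 30 | Any of three cohorts | 12 of 60 pooled |
|---|---|---|---|---|
| 2% | 0.0030 | 0.00003 | 0.6% | under 0.01% |
| 5% | 0.0362 | 0.0033 | 7.4% | under 0.01% |
| 8% | 0.1130 | 0.0293 | 24% | 0.3% |
| 10% | 0.1841 | 0.0732 | 38% | 1.5% |

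**The case against.** The strongest reply is that 7.10.1 is ambiguous rather than broken. The subheading parallels the one for individual subjects and may describe who is stopped, not who is counted. The event list is broad, so some events elsewhere are plausible. Any pooled rule is weak for a single arm. This stands in part. The impossibility needs four conditions together: a whole-study denominator, planned numbers, no replacements, and no listed event in the other 50 subjects. A reader might infer that the halt can never fire because of Cohort 3; the documents do not support that, since other arms' events count and replacement can carry the arm past 20%. What remains is the weakness at moderate arm rates shown in the table.

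A reader might also infer that Cohort 3 is unprotected. It is not. Individual stopping is mandatory, liver tests are frequent, sentinels are reviewed, and the sponsor, chief investigator and SRC have discretion to act. But these measures are individual, limited to sentinels, or discretionary. The Day 36 review is specified for Cohorts 1 and 2. Protocol 9.4 speaks of each cohort but ties the review to progression and gives no number. The same section points to a Trial Monitoring Plan and a Pharmacovigilance Plan, which are not among the documents and may say more.

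Finally, cohort thresholds are a design choice with a real false-trigger cost. That is right, and it counts against making the cohort trigger a full halt.

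**Conclusion.** The point holds in this form, and the rule should be fixed. The missing denominator is established from the text. If the denominator is the whole study, as the subheading suggests but does not state, events confined to High-dose + IC31 reach 16.7% of the planned total and at most 18.2% of those dosed, under the conditions above. With 2-5% assumed background and half the arm affected, the halt fires with probability 0.002-0.04. If the denominator is subjects dosed to date, one sentinel event in Cohort 1 is enough to stop the trial. The shares follow directly from the planned sizes and hold equally for 72 subjects. The probabilities depend on background rates that the documents do not give, and on independent events.

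**What to change.** Amend Protocol 7.10.1 in two places.

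1. State that the study-wide 20% is taken of the planned total, so that single early events do not halt the trial. Settle that total at the same time: the Trial Summary has about 60, section 1 has 72, and Table 3 lists 18, 36 and 18 randomisation numbers, which may only be replacement slots.

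2. Add a cohort-level trigger. When 20% of the cohort's planned size have a listed event, further dosing in that cohort pauses pending SRC review. On the Table 2 sizes this is 3 of 15, 6 of 30 and 3 of 15; on 18/36/18 it is 4, 8 and 4. Count on blinded data, keep the planned size fixed, and include events in replaced subjects.

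The cost is a wording amendment, with no extra patients or data. The downside is unnecessary pauses: 0.6%, 7.4% and 38% over the three cohorts at assumed background rates of 2%, 5% and 10%. That is why the cohort-level action should be a pause and not a full halt.

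The trigger has limits. It is weak in Cohort 2 when one arm is affected. With 4 of 18 in Cohort 3 (12 active, 6 control), detection at a 30% arm rate falls to 0.51-0.58. It protects only doses not yet given. The percentage itself remains a choice for the sponsor and SRC.
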